7.5.2 Secondary efficacy variables

The following secondary efficacy endpoints will be tested in the hierarchy below in order to preserve the overall alpha level:

1. Combined assessment of function and survival (CAFS) through 48 weeks
2. Time to respiratory event
3. Clinical Global Impression (CGI) through 48 weeks
4. Supine Borg CR 10 scale at 12 weeks
5. Slope of change in the ALSFRS-R respiratory domain through 48 weeks

The endpoints and their methods of analysis are described in the following sections. Endpoints and analyses that are not listed in the testing hierarchy are included for supportive purposes only.

7.5.2.1 Revised ALS Functional Rating Scale

The ALSFRS-R (Cedarbaum JM et al., 1999) includes 12 items: speech, salivation, swallowing, handwriting, cutting food and handling utensils, dressing and hygiene, turning in bed and adjusting sheets, walking, climbing stairs, dyspnea, orthopnea, and respiratory insufficiency. Each item will be scored from 0 to 4, with lower values indicating worse function. The variables derived will be the scores of the 12 separate items, the total scores of each subdomain (bulbar [items 1-3], fine motor [4-6], gross motor [7-9] and respiratory [10-12]) and the total score of ALSFRS-R.

The ALSFRS-R and its subdomains will be analysed through 48 weeks. The slope of decline for ALSFRS-R will be estimated using a random slope model. Statistical significance of the difference in slopes between the treatment groups will be tested. Additional analyses of the ALSFRS-R and its subdomains will be conducted using the MMRM and estimates for the treatment effect at each study visit will be obtained with model-based contrasts. Descriptive statistics over the course of the study will be reported for all items in the scale, as well as each subdomain and the total scale.

The following efficacy variables derived from the ALSFRS-R scores will also be assessed:

- Combined assessment of function and survival (CAFS; see 7.5.2.2).
- Time to decline from baseline in ALSFRS-R total score by $\geq 20\%$.
- Time to decline from baseline in an ALSFRS-R respiratory domain score (items 10–12).

- Time to continuous ventilator dependence (item $12 \leq 1$).

The methods of analysis for the time-to-event endpoints are described in 7.5.2.3. CAFS and its analysis are described further in section 7.5.2.2 below.

For use in subgroup analyses, two additional variables will be derived from the ALSFRS-R:

King's clinical stage is a staging system used to measure the clinical progression of the ALS disease across body system regions. Staging is not directly collected as part of the study. Instead, King's clinical stage will be estimated from the ALSFRS-R as follows (Balendra, 2014):

1. Respiratory failure (Item 10 = 0 or Item 12 < 4) \Rightarrow Stage 4b
2. Nutritional failure (answered item 5b) \Rightarrow Stage 4a
3. For lower stages, count the number of regions involved:
 - a. Bulbar (any of items 1–3 < 4)
 - b. Upper limbs (either of items 4 and 5a < 4)
 - c. Lower limbs (item 8 < 4)

King's stage is used to describe disease progression, and will be reported with descriptive statistics over the course of the study.

ALS progression rate at baseline will be calculated as the number of points missing from a full ALSFRS-R score (48) at baseline divided by the time (in months) between symptom onset and the baseline ALSFRS-R measurement.

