5. DETERMINATION OF SAMPLE SIZE

Sample size estimation is based primarily on supine SVC results from the study 3119001 LEVALS (Table 1). LEVALS had placebo-controlled data only up to 2 weeks, and therefore extrapolation of the results was needed. The placebo effect from phase II tirasemtiv trial BENEFIT-ALS (Shefner JM et al., 2016) was also evaluated.

Assuming a difference of at least 3.6% in change from baseline supine SVC between treatment groups and a common standard deviation of 10%, 164 evaluable subjects per group in a 1:1 allocation ratio have 90% power to detect a statistically significant difference in a two-sided, 5% α -level, two group T-test. Using a 2:1 allocation ratio, randomisation of 450 subjects to the study (approximately 300 levosimendan and 150 placebo treated subjects) allows for a total dropout rate of approximately 20%.

Table 1. Mean (SD) change from baseline SVC (supine) %-predicted in LEVALS

Treatment	2 weeks	12 weeks
Levosimendan 1 mg x 2	+2.4 (8.3)	-4.9
Levosimendan 1 mg x 1	+0.8 (8.6)	
Placebo	-3.6 (9.4)	-17.7 ¹
Placebo (BENEFIT-ALS)	-1.4	-8.5

¹ Extrapolated from the data

SD = standard deviation

Based on the dexpramipexole phase III study EMPOWER (Cudkowicz ME et al., 2013), a 12 point reduction in total ALSFRS-R score and a 15% mortality rate at 12 months can be assumed

in placebo treated patients. Assuming a 10 point decline in ALSFRS-R, with a standard deviation of 8 points, and a 20% relative improvement in survival, 450 patients provide approximately 80% simulated power to detect a statistically significant difference using a joint rank test. With 450 subjects and assuming a 48-week levosimendan event rate of 73% and hazard ratio of 0.70, time to respiratory event has approximately 70% power to detect a statistically significant difference using a log-rank test.

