6.2.2 Significance level and confidence intervals

Two-sided tests with a significance level of 5% will be used throughout the analyses. Corresponding 95% confidence intervals will be calculated for model-based contrasts, comparing the active treatment to placebo, using model-based standard error estimates.

The study has interim analyses that allow early stopping for futility, but not for efficacy. Therefore, we do not make adjustments to the significance levels in the final analyses.

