6.2.9 Multiple timepoints

The primary efficacy model will include all planned post-baseline visits up to the Week 12 visit. Additional analyses of primary efficacy will include all planned study visits. Included timepoints for other endpoints will be described separately. Baseline measurements of outcome variables will be included as covariates in the models. The MMRM will be used to estimate the covariance between measurements for a given subject, without assuming any specific structure a priori. Planned visit will be included as a factor in the model. For slope analyses, the actual study day of the visit will be used. All time-to-event analyses will be performed up to the first event only.

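### The ALSFRS-R slope models leave out the pre-treatment progression rate that the SAP already derives: possible lost efficiency, mainly for the supportive total-score slope

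*SAP*

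**What the plan says.** The fifth endpoint in the testing hierarchy of SAP 7.5.2 is "Slope of change in the ALSFRS-R respiratory domain through 48 weeks". The slope of the total score is also tested, but it lies outside the hierarchy and is therefore supportive. For the method, SAP 7.5.2.1 says "The slope of decline for ALSFRS-R will be estimated using a random slope model".

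The terms of that model are not written out and have to be assembled from elsewhere:

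- SAP 6.2.9 gives the general rule "Baseline measurements of outcome variables will be included as covariates in the models" and uses the actual study day in slope analyses.
- SAP 7.5.4.3 swaps the source of the randomisation strata in the respiratory-domain slope analysis, which implies that the stratum is a model term.
- SAP 7.5.4.9 adds riluzole use to that analysis as a sensitivity analysis, without interactions.

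SAP 7.5.2.1 also says "ALS progression rate at baseline will be calculated as the number of points missing from a full ALSFRS-R score (48) at baseline", divided by the months from symptom onset to that assessment. The rate is introduced for subgroup work. It appears in the baseline characteristics (7.2) and as two subgroup variables (6.2.14), one cut at 1 point per month and one by tertiles. It is in none of the sensitivity analyses in 7.5.4 and not in the imputation model in 6.2.5.

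**The concern.** When the outcome is a rate of change, the most natural baseline covariate is the earlier rate of change. A baseline score or a stratum entered as a main effect moves a subject's level. It does not explain why one subject declines faster than another, and that between-subject spread in slopes drives the standard error of the treatment-by-day contrast.

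The baseline score is also an incomplete stand-in for the rate. Inclusion criterion 6 of the protocol admits subjects 12 to 48 months from onset, so the same points lost at entry can mean rates that differ by a factor of 48/12 = 4. The sponsor already regards the rate as worth two subgroup analyses. If it predicts the on-study slope, the planned slope tests have wider standard errors than the collected data would allow.

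**Working it through.** **Where the rate is used.** Setting SAP 6.2.5, 6.2.9, 6.2.14, 7.2, 7.5.2.1 and 7.5.4 side by side, the rate enters only baseline tables and subgroup analyses. Those subgroup analyses cover three endpoints: the primary endpoint, time to respiratory event, and the total-score slope. The respiratory-domain slope is not one of them, so the rate enters no prespecified model of the fifth hierarchical endpoint.

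**The plan's own sample size.** SAP 5 gives "Assuming a difference of at least 3.6% in change from baseline supine SVC between treatment groups and a common standard deviation of 10"%, and states that "164 evaluable subjects per group in a 1:1 allocation ratio have 90% power". With two-sided alpha of 5% (SAP 6.2.2), n = 2 × (1.960 + 1.282)² × 10² / 3.6² = 162.2, so 163 per group. The noncentral t power at 164 per group is 90.2%. At 2:1 the requirement is 122 + 244 = 366, so 450 allows 1 − 366/450 = 18.7% dropout. The stated figures reproduce. No effect, SD or power is stated for any ALSFRS-R slope.

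**Illustration on the total score.**

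- From SAP 5: a 12-point decline on placebo and a 10-point decline, read here as the levosimendan group, so a difference of 2 (taken over 48 weeks); SD of change 8; "Using a 2:1 allocation ratio, randomisation of 450 subjects to the study (approximately 300 levosimendan and 150 placebo treated subjects").
- From the protocol's schedule: ALSFRS-R at weeks 0, 4, 8, 12, 18, 24, 30, 36, 42 and 48. With time in units of 48 weeks, Sxx = 1.0675.
- Assumed: residual SD 2, and a range for r, the correlation of the rate with the true on-study slope.

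Keeping the SD of the 48-week change at 8 gives a between-subject slope variance of 64 − 2 × 2² = 56. The variance of an estimated slope is then

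V(r) = 56 × (1 − r²) + 4/1.0675 = 56 × (1 − r²) + 3.75.

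The standard error of the difference is √V × √(1/300 + 1/150) = 0.1 × √V, and power is Φ(2/SE − 1.96). Without the rate, V = 59.75, SE = 0.773 and power = Φ(0.627) = 73.5%.

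| r | V(r) | Variance reduction | Power | Gain (points) | Equivalent unadjusted N (450 × 59.75/V) |
|---|---|---|---|---|---|
| 0.1 | 59.19 | 0.9% | 73.9% | 0.4 | 454 |
| 0.2 | 57.51 | 3.7% | 75.1% | 1.6 | 468 |
| 0.3 | 54.71 | 8.4% | 77.2% | 3.7 | 491 |
| 0.4 | 50.79 | 15.0% | 80.1% | 6.6 | 529 |
| 0.5 | 45.75 | 23.4% | 84.1% | 10.6 | 588 |

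**Sensitivity.** With 20% dropout (240 and 120 subjects), power of 63.8% rises to 67.7% at r = 0.3 and 75.3% at r = 0.5. Residual SDs from 1 to 3 move the starting power from 71.3% to 77.4%. The gain is then 3 to 4 points at r = 0.3 and 9 to 11 points at r = 0.5.

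**Which term does the work.** Random slope models were fitted to simulated trials (46 data sets at r = 0.3 and 47 at r = 0.5). The mean standard errors of the slope difference were:

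| r | No rate term | Rate as main effect only | Rate and rate-by-time |
|---|---|---|---|
| 0.3 | 0.780 | 0.780 | 0.749 |
| 0.5 | 0.779 | 0.779 | 0.685 |

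Only the interaction with time recovers precision.

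**The case against.** The strongest reply is that this is an optional covariate whose benefit cannot be shown from the documents. Much of that stands:

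- No correlation is given. At r of 0.2 or less the gain is under 2 points, which few would notice.
- The rate is built from the total score, whereas the endpoint in the hierarchy uses only 3 of the 12 items. The derived rate is not that endpoint's own pre-treatment slope, and the documents give no effect, SD or correlation for the domain.
- The test is fifth in line. Taking the SAP's stated powers of about 80% and 70% for the first two endpoints at face value, and assuming independence, both succeed with probability 0.80 × 0.70 = 0.56, before CGI and Borg CR10 are counted. Positive correlation between the tests would raise this.
- The respiratory-domain slope is analysed on multiply imputed data. Adding the rate to the analysis model alone could weaken its association with the imputed values.

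A reader might infer that a hierarchical test is certainly underpowered, or that its result would be biased. The documents support neither. A gain from 80% to 90% power can be produced, but it needs r = 0.5, perfectly reliable slopes and a reference power that the SAP never states for slopes. A reader might also conclude that the planned adjustments are main effects only; because the model is not written out, the most that can be said is that no interaction with time is stated. A stratum-by-day term might seem a natural companion, but the 8-level factor of SAP 6.2.1 would add 7 parameters, with no benefit shown.

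What the reply does not remove is that the rate is already derived, is absent from every slope model, and costs little to use.

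**Conclusion.** The omission is confirmed by the text. The consequence is possible lost efficiency; the validity of the tests is not in question. Under the illustration's assumptions, the total-score slope would gain about 0.4 points of power at r = 0.1, 1.6 at 0.2, 3.7 at 0.3 and 10.6 at 0.5, from 73.5%. These figures rest on reading the 10-point decline as the levosimendan group, on the assumed residual SD of 2, on complete follow-up, and on an r that the documents do not supply. They do not model imputation.

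The main beneficiary is the supportive total-score slope. For the respiratory-domain slope the gain cannot be quantified, may be smaller, and counts only if the four earlier endpoints succeed. This is a worthwhile refinement, not a necessary correction.

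**What to change.** Before unblinding, write out the random slope models for the ALSFRS-R total score and respiratory domain. In each, add the continuous ALS progression rate at baseline and its interaction with study day. Keep treatment-by-day as the tested contrast, and do not add stratum-by-day. Add the rate to the section 6.2.5 imputation model for the ALSFRS-R items, so that the imputation and analysis models agree. State whether the continuous rate stays in the model for the two progression-rate subgroup analyses of the total-score slope.

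The cost is SAP wording, two terms per slope model and one more variable in the imputation code. No new data are needed, because symptom onset is recorded at screening. The downside is small: slightly larger models that rely on the reported onset date, which already determines eligibility.

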7.5.2.2 Combined assessment of function and survival

Combined assessment of function and survival (CAFS) is a rank score based on the subject's survival time and change in ALSFRS-R score (Berry JD et al., 2013). A higher CAFS score for a subject indicates a better outcome relative to other subjects in the study.

To find the CAFS score, a sum score is calculated for each subject by comparing their status to all other subjects. In each individual comparison, the subject's score is incremented if they fared better than the other, and decremented if they fared worse. If their outcomes are equal, the score remains unchanged. This process produces an equivalent ordering to simply ranking the subjects based on their outcomes, and breaking ties with the given hierarchy of outcomes. The ordering between the subjects' outcomes is determined first by survival status: if both subjects died, then by survival time; and if both subjects survived, finally by the change from baseline ALSFRS-R score. Once these scores have been calculated for all subjects, they are ranked, from lowest (died first) to highest (best ALSFRS-R outcome among those who survived), yielding the final CAFS score used as the endpoint.

CAFS is analysed using the Wilcoxon-Mann-Whitney test to compare mean scores between the treatment groups at the Week 48 study visit. Statistical significance will be assessed based on the confidence interval derived for the Hodges-Lehmann estimator. In additional analyses, CAFS will also be assessed at the Week 12 and Week 24 study visits.

SAS code in the following fashion will be used to conduct the analysis:

```
proc npar1way data = ADEFF wilcoxon hl;
```

```
where ITTFL = "Y" and PARAMCD = "CAFS" and AVISIT = "Week 48";  
class TRTP;  
var AVAL;  
run;
```

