8.4.3 Analysis of efficacy

The primary efficacy variable SVC (supine) will be compared between the treatment arms using the MMRM with between subject effects for treatment, centre and randomisation strata, time as within subject effect, and baseline value (visit 1) as a covariate. Primary efficacy will be evaluated at 12 weeks using contrasts to obtain estimates from the primary model including all SVC measurements prior to 12 weeks. Any missing data will be imputed using multiple imputation method. Effect of missing data imputation will be evaluated analysing observed data only and estimating the slope of decline using the random slope model. Several sensitivity subgroup analyses will be performed and defined in the SAP. Additional evaluations will be performed including all data through 48 weeks, using the MMRM.

DNO 090017ff823c9bac / 1.0 Approved 46 / 58

SD = standard deviation

Secondary efficacy endpoints will be tested in following hierarchy to preserve the overall alpha level:

- 1. Combined assessment of ALSFRS-R function and survival through 48 weeks
- 2. Time to respiratory event through 48 weeks
- 3. CGI through 48 weeks
- 4. Supine Borg CR 10 scale at 12 weeks
- 5. Slope of decline in respiratory function of ALSFRS-R through 48 weeks

The efficacy variables time to respiratory event, time to NIV or death, time to SVC (supine) decline of 20%, time to SVC (supine) \leq 50% of predicted, time to ALSFRS-R total score decline of 20% and time to decline in ALSFRS-R respiratory domain will be evaluated using the Cox's proportional regression model. The model will include effect for treatment and will be adjusted for randomisation strata. Premature discontinuations will be censored from the analyses. Censoring rules will be defined in the SAP.

The efficacy variables ALSFRS-R total score and its subdomain scores will be performed through 48 weeks. Primary analysis will combine change from baseline to 48 weeks and survival through 48 weeks in joint rank analysis (Berry JD et al., 2013) using Wilcoxon-Mann-Whitney test. Slope of decline will be estimated using the random slope model. Additional analyses will be conducted using the MMRM and estimates for individual time points will be done using contrasts. Imputation of missing data using the multiple imputation method will be considered.

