6.2.13 Interim analyses and data monitoring

Two interim analyses will be conducted: first when approximately 50% of the subjects, and second when all of the subjects have completed their Week 12 study visit (Visit 5).

An independent DSMB will perform and evaluate the interim/futility analyses and make recommendations for the study conduct. The DSMB will have access to the treatment code through an independent reporting statistician, and the DSMB will have a possibility review any unblinded information in a separate closed session. Details on the composition and responsibility of the DSMB are outlined in a DSMB charter. Based on the futility analyses the DSMB will give its recommendation “continue” or “not continue” the study to the Orion Executive Committee (OEC).

Futility will be evaluated in the primary efficacy endpoint, and the time to respiratory event endpoint. We estimate that approximately 40% and 85% of the respiratory events will have accumulated at the time of the planned interim analyses.

In addition the SVC and respiratory event endpoints, accumulated data for the ALSFRS-R, CGI and Borg CR 10 will be summarized at the interim analyses.

Non-binding stopping criteria will be based on O’Brien-Fleming type boundaries (Lan GKK et al., 1983, O’Brien PC et al., 1979) and are detailed in the DSMB SAP.

As the interim analyses only allow early stopping for futility, not for efficacy or sample size re-estimation, adjustments to significance levels are not made in the final analyses.

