6.2.14 Subgroups

Subgroups will be analysed for evidence of a differential treatment effect. A treatment-by-subgroup interaction term will be added to the statistical model, and the stratification factor, if present, will be removed. Subgroups defined by the following variables will be investigated:

1. Age (< 65, 65–74, ≥ 75)
2. Sex (male, female)
3. Race (white, non-white)
4. Country
5. Region (North America, rest of the world)
6. Site of onset (bulbar, spinal)
7. Edaravone use (yes, no)
8. Riluzole use (yes, no)
9. Combination of edaravone and riluzole use (4 groups)
10. Below median disease duration (time from symptom onset to randomization)
11. Above median time from symptom onset to diagnosis
12. Acetylation status (slow, fast; see 7.7)
13. Renal impairment status (see 7.9.3)
14. Hepatic impairment status (see 7.9.3)
15. Below median SVC (sitting) at screening
16. Below median SVC (supine) at baseline
17. King's clinical stage at baseline (see 7.5.2.1)
18. Below median ALSFRS-R at baseline
19. ALS progression rate at baseline (< 1 point/month, ≥ 1 point/month)
20. ALS progression rate at baseline (observed tertiles)
21. Dose change category (see section 7.4)

Subgroup analyses will be performed for the primary efficacy endpoint, the time to respiratory event endpoint, and the slope of change in the ALSFRS-R total score endpoint. Ad-hoc analyses of other endpoints may also be performed, and included in the study report.

Summary of AEs and AESIs will be presented in the subgroups of: age; sex; race; BMI; edaravone use; riluzole use; acetylation status; baseline medical history groups of interest (see 7.3); baseline renal and hepatic impairment status; and baseline King's clinical stage.

Adverse events will be summarised by patients having heart rate increase related dose changes. Drug-drug-interactions with medication groups of interest (see 7.10.1) will be evaluated for blood pressure, pulse rate, and QT interval. Dose changes will be further presented by acetylation status.

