7.5.2.3 Respiratory event and other time-to-event endpoints

A 'time to respiratory event' composite endpoint consists of the following events:

- A decrease of one or more points from baseline in any of the ALSFRS-R respiratory function subdomain scores (items 10–12).
- Starting non-invasive mask ventilation (NIV).
- Meeting 'protocolised' criteria for NIV: SVC (supine) $\leq 50\%$ predicted.
- Invasive mechanical ventilation by intubation.
- Invasive mechanical ventilation by tracheostomy.
- Death.

Time to respiratory event is reached whenever any of the criteria has first been met.

The following time-to-event secondary efficacy variables will be evaluated using Cox's proportional hazards regression:

1. Time to tracheostomy, continuous ventilator dependence, or death (TRCVDDTH)
2. Time to NIV or death (NIVDEATH)
3. Time to respiratory event (RESPEVNT)

Individual components of all the composite endpoints will be analysed in the same fashion:

1. Time to continuous ventilator dependence (ALSFRS-R item 12 ≤ 1 ; CVD)
2. Time to decline from baseline in any ALSFRS-R respiratory domain score (FRSBR1D)
3. Time to SVC (supine) $\leq 50\%$ of predicted (SVC50PP)
4. Time to non-invasive mask ventilation (NIV)
5. Time to intubation (INTUB)
6. Time to tracheostomy (TRACH)
7. Time to death (DEATH)

As will these additional endpoints derived from the SVC and ALSFRS-R values:

1. Time to decline from baseline SVC (supine) by $\geq 20\%$ (SVC20PD)
2. Time to decline from baseline ALSFRS-R total score by $\geq 20\%$ (FRS20PD)
3. Time to continuous use of NIV during the night (ALSFRS-R item 12 ≤ 2)

The data for the time-to-event variables will be stored in the ADTTE dataset with parameter names corresponding to those in parentheses above.

The analysis model will include an effect for treatment, and will be adjusted for randomization strata. Premature discontinuations will be treated as right-censored in the analyses. Censoring rules for different scenarios are described in **Error! Reference source not found..** For the purpose of determining the end date, survival and ventilation status are considered to be assessed daily; ALSFRS-R and SVC measurements are assessed only on study visits. For composite

endpoints, the date of last assessment is defined to be the latest date at which the endpoint can be fully assessed: that is, the earliest date in the set of latest assessments of each of its component endpoints.

Table 2. Censoring rules for time-to-event analyses.

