Scenario	Censored	End date
Event criteria fulfilled	No	Date of endpoint assessment
Event criteria fulfilled at baseline	Yes	Date of randomization
Event criteria never assessed	Yes	Date of randomization
Completed Week 48 without event	Yes	Date of last endpoint assessment
Discontinued study	Yes	Date of last endpoint assessment
Discontinued study treatment (1 day after*)	Yes	Date of last endpoint assessment
Died, when death not part of event criteria	Yes	Date of last endpoint assessment
Died, when death is part of event criteria	No	Date of death

*) to account for potential events following immediately after the study treatment discontinuation.

SAS code in the following fashion will be used to fit the statistical models:

```
proc phreg data = ADTTE;
  where ITTFL = "Y" and PARAMCD = "RESPEVNT";
  class TRTP(ref = "PLACEBO") STRATAR;
  model AVAL * CNSR(1) = TRTP STRATAR / ties = efron rl;
run;
```

For descriptive purposes, Kaplan-Meier survival curves will be plotted in addition to the statistical analysis results from the Cox models. Also, restricted mean survival time (RMST) will be described graphically at 14-day intervals from start of follow-up up to 48 weeks. These analyses are used to visually inspect the plausibility of the proportional hazards assumption.

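### CAFS is tested with no strata or baseline covariates, and the respiratory-event Cox model omits baseline supine SVC and ALSFRS-R; adjusting both is a low-cost improvement of uncertain size

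*SAP*

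**What the plan says.** **CAFS (step 1).** SAP 7.5.2.2: "CAFS is analysed using the Wilcoxon-Mann-Whitney test to compare mean scores between the treatment groups at the Week 48 study visit". The SAS code is a two-sample rank procedure with TRTP as the only class variable. Significance is read from the Hodges-Lehmann interval, pooled over imputations. Protocol 8.4.3 agrees: "Primary analysis will combine change from baseline to 48 weeks and survival through 48 weeks in joint rank analysis", by Wilcoxon-Mann-Whitney.

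**Time to respiratory event (step 2).** SAP 7.5.2.3: "The analysis model will include an effect for treatment, and will be adjusted for randomization strata". The code is "model AVAL * CNSR(1) = TRTP STRATAR / ties = efron rl". Protocol 8.4.3 agrees: "The model will include effect for treatment and will be adjusted for randomisation strata".

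**Elsewhere in the plan.**
- SAP 6.2.1 builds one eight-level stratum for adjusting the models.
- The primary MMRM (SAP 7.5.1.1) uses that stratum and baseline supine SVC.
- SAP 6.2.9 says in general terms that baseline outcome values enter the models as covariates. In context this can be read as limited to the MMRM, and neither specification above does it.
- SAP 7.5.4 has no sensitivity analysis that adds these terms to either test. The riluzole adjustment covers only the primary MMRM and the respiratory-domain slope.
- SAP 6.2.14 uses median splits of baseline SVC and ALSFRS-R for the respiratory event, but "A treatment-by-subgroup interaction term will be added to the statistical model, and the stratification factor, if present, will be removed". These are interaction analyses, not an adjusted main test.
- SAP 7.5.2.1: "Additional analyses of the ALSFRS-R and its subdomains will be conducted using the MMRM". These are supportive and do not replace the test at step 1.

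**The concern.** The hierarchy in SAP 6.2.3 and 7.5.2 makes these two tests gatekeepers for CGI, Borg CR10 and the respiratory-domain slope. Planning power is already limited: about 80% and 70% in SAP 5.

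The omitted variables are plausibly prognostic on the documents' own account:
- Protocol 1.2.1 cites supine vital capacity as a predictor of survival. Death is the lowest tier of CAFS and a component of the respiratory event.
- A supine SVC at or below 50% predicted is itself a respiratory event.
- Baseline ALSFRS-R and progression rate are already derived for subgroup use.

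No new data are needed. The question is how much power is left unused at the two steps where a miss costs most.

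**Working it through.** **1. Planning figures (SAP 5).** Inputs: 300 vs 150, two-sided 5%.

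*CAFS.* ALSFRS-R decline 12 vs 10 points, SD 8; deaths 15% vs 12% (20% relative reduction). On this literal reading the joint rank test has 60-65% simulated power, not the stated 80%. A 2.5-point difference (12.5 vs 10) gives 80%. The sponsor's simulation settings are not stated.

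*Respiratory event.* With 73% events on levosimendan and HR 0.70:
- placebo rate = 1 - 0.27^(1/0.70) = 84.6%
- events = 300 × 0.73 + 150 × 0.846 ≈ 346
- z = √(346 × 2/9) × |ln 0.70| - 1.96 = 8.77 × 0.357 - 1.96 = 1.17, so power is about 88%, not 70%.

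Because neither stated power is reproduced, gains are shown from both starting points.

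**2. Dependence of one component on baseline.** Assume SD 10 (SAP 5) and a week-12 change independent of baseline. Then P(SVC ≤ 50) = Φ((50 - b + d)/10), where b is baseline supine SVC and d the mean placebo decline in SAP Table 1.

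| b | d = 8.5 | d = 17.7 (extrapolated) |
|---|---|---|
| 60 | Φ(-0.15) = 44% | Φ(0.77) = 78% |
| 70 | Φ(-1.15) = 12.5% | Φ(-0.23) = 41% |
| 80 | Φ(-2.15) = 1.6% | Φ(-1.23) = 11% |

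**3. CAFS: Wilcoxon against ANCOVA on the ranks.** One prognostic baseline score, one null covariate, eight non-prognostic strata, complete data; 5,000-6,000 runs. R² is an assumption.

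| R² | Wilcoxon | Rank ANCOVA | Change (points) |
|---|---|---|---|
| 0.002 | 64.1%; 62.3% | 63.7%; 61.6% | about -0.5 |
| 0.029 | 62.6% | 63.0% | +0.4 |
| 0.055 | 63.0% | 64.6% | +1.6 |
| 0.104 | 60.7% | 65.0% | +4.3 |
| 0.144 | 59.9% | 66.8% | +6.9 |
| 0.206 | 60.5% | 70.2% | about +10 |

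With the ALSFRS-R effect scaled to 2.55 points, so that the start is near 80%:

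| R² | Wilcoxon | Rank ANCOVA | Change (points) |
|---|---|---|---|
| 0.002 | 80.0% | 78.6% | -1.4 |
| 0.054 | 79.4% | 80.5% | +1.1 |
| 0.103 | 78.6% | 82.7% | +4.1 |
| 0.205 | 78.7% | 86.3% | +7.6 |

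The standard error of each change is 0.3-0.6 points. Under the null, Wilcoxon rejected 4.8-5.2% and rank ANCOVA 4.9-5.4%. A separately written simulation with one covariate gave similar gains: 64.7% to 67.3%, 64.2% to 69.0% and 63.5% to 74.5% at latent R² 0.05, 0.10 and 0.20.

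**4. Cox model.** The planning HR is paired with a log-rank test, so 0.70 was treated as the marginal HR and the conditional HR was solved to match. One prognostic and one null covariate, strata omitted, 4,000 runs.

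| Covariate HR per SD | 300:150, without → with | 188:94, without → with |
|---|---|---|
| 1.0 | 88.5% → 88.3% | 70.9% → 71.0% |
| 1.2 | 88.8% → 89.9% | 70.7% → 72.4% |
| 1.35 | 88.2% → 91.4% | 71.4% → 75.3% |
| 1.5 | 89.3% → 92.8% | 70.2% → 77.9% |

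The 188:94 size is not planned. It is used only to start near the stated 70%. The standard error of each change is 0.2-0.6 points, and null rejection was 4.7-5.7% for both models. If the conditional HR is held at 0.70 instead, the gap is wider (86.0% vs 90.9% at HR 1.49 per SD, 300:150), partly because the unadjusted HR shrinks to 0.715.

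**The case against.** The strongest reply is that nothing is broken. Both tests are valid, prespecified and consistent with the protocol, and CAFS already ranks change from baseline. The benefit cannot be sized from the documents and runs from a small loss to about 10 points. For the Cox model at the planned size it is at most about 4 points from a high start. All of this stands, and it is why the point concerns efficiency and why CAFS has priority.

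Other objections stand in part:
- The SVC illustration covers one component, and subjects meeting an event criterion at baseline are censored at randomisation (SAP Table 2). Any benefit therefore comes from those starting above the threshold.
- The CAFS simulation did not hold the marginal effect fixed: unadjusted power drifts from 64% to 60% as R² rises. The within-row differences are the relevant figures.
- Dropout and multiple imputation were not simulated.
- Progression rate is calculated from baseline ALSFRS-R, so the two proposed CAFS covariates are related. This limits their joint information but does not invalidate the ANCOVA.

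The subgroup models and SAP 6.2.9 do not close the gap. The former drop the strata and test interactions; the latter is not carried into either specification.

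**Conclusion.** The point holds as an efficiency improvement that should be made. CAFS has neither stratum nor baseline covariate, and the respiratory-event model has stratum only. No analysis in the plan gives an adjusted test at either step.

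The expected gain for CAFS is roughly +1 to +10 points for R² between about 0.05 and 0.21, against a loss of 0.5-1.4 points if the covariates carry no information. For the Cox model it is 0 to +4 points at 300:150, or 0 to +8 if true power is near the stated 70%. These ranges rest on assumed covariate strength, complete data and the planning effects in SAP 5. Where the real covariates fall is unknown. Confidence is medium.

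**What to change.** Settle the following before unblinding.

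1. **CAFS.** Within each imputed data set, analyse the CAFS ranks by ANCOVA with treatment, STRATAR, baseline ALSFRS-R and baseline progression rate. Pool the treatment difference by Rubin's rules. Keep the planned Wilcoxon/Hodges-Lehmann analysis as sensitivity. Add progression rate to the CAFS imputation model, since the variable list in SAP 6.2.5 omits it.
2. **Time to respiratory event.** Add baseline supine SVC and baseline ALSFRS-R total to TRTP and STRATAR. Keep the strata-only model as sensitivity. Check that the imputation models for the components carry the same baselines.
3. **Documentation.** List both changes in SAP 7.11 and reconcile SAP 6.2.9 with the two specifications. Check the DSMB SAP, because "Futility will be evaluated in the primary efficacy endpoint, and the time to respiratory event endpoint".

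The programming is small, but the cost goes beyond code. Both changes depart from protocol 8.4.3. The Cox hazard ratio becomes conditional on more covariates, which is a different estimand and not a bias correction. The CAFS summary becomes an adjusted mean-rank difference. The revision history says Hodges-Lehmann inference was adopted to support pooling, so that choice must be revisited; rank-ANCOVA estimates can also be pooled. A draft SAP went to FDA, so the change may need to be communicated.
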